2.2 Secondary

2.21 To determine the rates of best tumor response at the end of the first two treatment cycles of pazopanib in non clear cell metastatic renal cell cancer patients.

2.22 To determine the benefit of pazopanib in increasing progression free survival time.

2.23 To describe toxicity profile of pazopanib in non clear cell metastatic renal cell cancer patients.

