3.0 Patient Eligibility

3.1 Inclusion Criteria

3.11 Age \geq 18 years

3.12 Histological confirmation of non-clear cell renal cancer (including Chromophilic (papillary), Chromophobic, Oncocytic, sarcomatoid, Collecting duct (Bellini's duct), translocation-type carcinoma or medullary renal cell carcinoma.

3.13 Up to one prior treatment for metastatic non clear cell carcinoma is allowed prior to registration as long as the agent used to treat was not pazopanib.

3.14 Measurable or non-measurable metastatic disease as defined in Section 11.0.

3.15 ECOG Performance Status (PS) 0, 1 or 2 (Appendix II).

3.16 The following laboratory values obtained \leq 14 days prior to registration.

- ANC \geq 1500
- PLT \geq 100,000
- HgB $>$ 9.0 g/dL. NOTE: Subjects may not have had a transfusion within 7 days of registration.)
- Total Bilirubin $<$ 1.5 x ULN
- Alanine amino transferase (ALT) \leq 2.5 X ULN. NOTE: Concomitant elevations in bilirubin and ALT above 1.0 x ULN (upper limit of normal) is not permitted.

- Aspartate aminotransferase (AST) $\leq 2.5 \times$ ULN. Note: Concomitant elevations in bilirubin and AST above $1.0 \times$ ULN (upper limit of normal) is not permitted.
- Urine Protein to Creatinine Ratio (UPC; appropriate appendix) (UPC) < 1
NOTE: If UPC ≥ 1 , then a 24-hour urine protein must be assessed. Subjects must have a 24-hour urine protein value < 1 g to be eligible.
- Prothrombin time (PT) or international normalized ratio (INR) $\leq 1.2 \times$ ULN NOTE: Subjects receiving anticoagulant therapy are eligible if their INR is stable and within the recommended range for the desired level of anticoagulation

3.17 A female is eligible to enter and participate in this study if she is of:

a. Non-childbearing potential (i.e., physiologically incapable of becoming pregnant), including any female who has had:

- A hysterectomy
- A bilateral oophorectomy (ovariectomy)
- A bilateral tubal ligation
- Is post-menopausal

Subjects not using hormone replacement therapy (HRT) must have experienced total cessation of menses for ≥ 1 year and be greater than 45 years in age, OR, in questionable cases, have a follicle stimulating hormone (FSH) value > 40 mIU/mL and an estradiol value < 40 pg/mL (< 140 pmol/L).

Subjects using HRT must have experienced total cessation of menses for ≥ 1 year and be greater than 45 years of age OR have had documented evidence of menopause based on FSH and estradiol concentrations prior to initiation of HRT

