 - History of abdominal fistula, gastrointestinal perforation, or intra-abdominal abscess ≤ 28 days prior to registration.
 - Clinically significant gastrointestinal abnormalities that may affect absorption of investigational product including, but not limited to:
 - Malabsorption syndrome
 - Major resection of the stomach or small bowel.
- 3.29c Corrected QT interval (QTc) > 480 msec using Bazett's formula.
- 3.29d Receiving any medications or substances with risk of torsades de pointes (see Appendix II). Note: medications or substances on the list "Drugs with Risk of Torsades de Pointes" are prohibited. Medications or substances on the list "Drugs with Possible or Conditional Risk of Torsades de Pointes" may be used while on study with extreme caution and careful monitoring.
- 3.29e Known endobronchial lesions and/or lesions infiltrating major pulmonary vessels and/or hemoptysis in excess of 2.5 mL (or one half teaspoon) ≤ 8 weeks of registration
- 3.29f Treatment with any of the following anti-cancer therapies: radiation therapy, surgery or tumor embolization, chemotherapy, immunotherapy, biologic therapy, investigational therapy or hormonal therapy ≤ 14 days prior to registration.
- 3.39g Prior autologous or allogeneic organ or tissue transplantation.
- 3.39h Elective or planned major surgery to be performed during the course of

the trial.

- 3.39i Receiving any medications or substances that are **strong or moderate inhibitors** of CYP3A4 (for a listing of medications or substances see Appendix VI).

Use of the following strong or moderate inhibitors are prohibited ≤ 7 days prior to registration.

- 3.39j Receiving any medications or substances that are **inducers** of CYP3A4 (for a listing of medications or substances see Appendix VI).

Use of inducers are prohibited ≤ 7 days prior to registration.

4.0 Test Schedule	Active Monitoring Phase					
	≤28 days prior to registration	≤14 days prior to registration	Day 1 ⁴ , Every cycle	On interval weeks 2, 6, 10	Every other cycle	End of treatment
Tests and procedures						
Informed Consent	X					
History and exam, Wt, PS			X			X
Adverse event assessment			X			
Height		X				
Pregnancy test		X ²				
Vital Signs, including temperature		X	X			X
Echo (2D M-Mode)	X ^R				X ⁸	
Hematology CBC with diff, platelets		X	X ^{R,6}			X
Chemistries ¹		X	X ^{R,6}	X ⁹		X
UPC Urine		X				
Thyroid Function Test (TSH)		X ^R			X ^R	
Coagulation Test: PT, PTT		X	X			
CT Head/MRI		X ^R				

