13.0 Treatment/Follow-up Decision at Evaluation of Patient

- 13.1 Patients who are CR, PR, or SD will continue treatment per protocol.
- 13.2 Patients who develop PD while receiving therapy will go to the event-monitoring phase.
- 13.3 Patients who go off protocol treatment for reasons other than PD will go to the event-monitoring phase per Section 18.0.
- 13.4 Patients who develop non-CNS PD at any time should go to event monitoring.
- 13.5 A patient is deemed *ineligible* if after registration, it is determined that at the time of registration, the patient did not satisfy each and every eligibility criteria for study entry. The patient may continue treatment off-protocol at the discretion of the physician as long as there are no safety concerns, and the patient was properly registered. The patient will go directly to the event-monitoring phase of the study (or off study, if applicable).
- If the patient received treatment, all data up until the point of confirmation of ineligibility must be submitted. Event monitoring will be required per Section 18.0 of the protocol.
 - If the patient never received treatment, on-study material must be submitted. Event monitoring will be required per Section 18.0 of the protocol.
- 13.6 A patient is deemed a *major violation*, if protocol requirements regarding treatment in cycle 1 of the initial therapy are severely violated that evaluability for primary end point is questionable. All data up until the point of confirmation of a major violation must be submitted. The patient will go directly to the event-monitoring phase of the study. The patient may continue treatment off-protocol at the discretion of the physician as long as there are no safety concerns, and the patient was properly registered. Event monitoring will be required per Section 18.0 of the protocol.

- 13.7 A patient is deemed a cancel if he/she is removed from the study for any reason before any study treatment is given. On-study material and the End of Active Treatment/Cancel Notification Form must be submitted. The patient will go directly to the event-monitoring phase of the study, and event monitoring will be required per Section 18.0 of the protocol.

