16.0 Statistical Considerations and Methodology

- 16.1 Overview: This protocol will assess the efficacy of pazopanib in patients with non-clear cell metastatic renal cancer using a one-stage phase II study design.
- 16.11 Primary Endpoint: The primary endpoint of this trial is the 12-month overall survival rate. A “12-month overall survivor” will be considered synonymous with “success”, unless otherwise specified. A patient is considered to be a 12-month survivor if the patient lives 12 months from registration (note, all deaths prior to 12 months, regardless of cause, will be considered a failure). All patients meeting the eligibility criteria who have signed a consent form and have begun treatment will be evaluable for the primary endpoint. All eligible patients will be followed until death or a minimum of 2 years.
- 16.2 Statistical Design:
- 16.21 Decision Rule: The largest success proportion where the proposed treatment regimen would be considered ineffective in this population is 55%, and the smallest success proportion that would warrant subsequent studies with the proposed regimen in this patient population is 75%. The one-stage design based on properties of the binomial distribution uses 39 patients to test the null hypothesis that the true success proportion in a given patient population is at most 55%.
- 16.22 Sample Size: There will be 35 evaluable patients accrued onto this study unless undue toxicity is encountered. We anticipate accruing an additional 4 patients to account for ineligibility, cancellation, major treatment violation, or other reasons.
- 16.23 Accrual Time and Study Duration: The anticipated accrual rate is approximately 1-2 patients per month, based on the incidence of tumor type and the potential to accrue at Mayo Clinic sites (Mayo Clinic Rochester, Mayo Clinic Florida and Mayo Clinic Arizona). Therefore, the accrual period for this phase II study is expected to be 24 months. The final analysis can begin approximately 36 months after the trial begins, i.e. as soon as the last patient has been observed for 12 months.

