16.32 Definitions and Analyses of Secondary Endpoints

- 16.321 A tumor response is defined to be a CR or PR noted as the objective status on 2 consecutive evaluations at least 8 weeks apart. Tumor response will be evaluated. All patients meeting the eligibility criteria who have signed a consent form and have begun treatment will be evaluable for response.
- 16.322 Progression-free survival is defined as the time from registration to the earliest date documentation of disease progression or death. Kaplan-Meier curve will be used to estimate progression-free survival time.
- 16.323 Adverse events: All eligible patients that have initiated treatment will be considered evaluable for assessing adverse event rate(s). The maximum grade for each type of adverse event will be recorded for each patient, and frequency tables will be reviewed to determine patterns. Additionally, the relationship of the adverse event(s) to the study treatment will be taken into consideration.
- 16.324 Observation Phase: Retreatment of patients who have relapsed will be left to the discretion of the treating physician. Statistical analysis of the observational phase data for these patients will be of a descriptive nature.

16.4 Data & Safety Monitoring:

16.41 The study chair(s) and the study statistician will review the study at least twice a year to identify accrual, adverse event, and any endpoint problems that might be developing. The Mayo Clinic Cancer Center (MCCC) Data Safety Monitoring Board (DSMB) is responsible for reviewing accrual and safety data for this trial at least twice a year, based on reports provided by the MCCC Statistical Office.

16.42 Adverse Event Stopping Rules: The stopping rules specified below are based on the knowledge available at study development. We note that the Adverse Event Stopping Rule may be adjusted in the event of either (1) the study re-opening to accrual or (2) at any time during the conduct of the trial and in consideration of newly acquired information regarding the adverse event profile of the treatment(s) under investigation. The study team may choose to suspend accrual because of unexpected adverse event profiles that have not crossed the specified rule below.

Accrual will be temporarily suspended to this study if at any time we observe events considered at least possibly related to study treatment (i.e. an adverse event with attribute specified as “possible”, “probable”, or “definite”) that satisfy the following:

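### Adverse-event rates cover only eligible treated patients, so a dosed patient later found ineligible is left out of the toxicity tables

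*Combined protocol and SAP*

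**What the plan says.** Section 16.323 defines who counts in the adverse-event analysis: "All eligible patients that have initiated treatment will be considered evaluable for assessing adverse event rate(s". Two conditions must both hold, eligibility and a start of treatment. Each patient's worst grade for each event type is then tabulated.

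Section 13.5 allows eligibility to be withdrawn from a patient who is already registered. The test is whether "it is determined that at the time of registration, the patient did not satisfy each and every eligibility criteria for study entry". It provides for the case where dosing has already happened: "If the patient received treatment, all data up until the point of confirmation of ineligibility must be submitted".

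The tables in 16.323 serve secondary goal 2.23: "To describe toxicity profile of pazopanib in non clear cell metastatic renal cell cancer patients". I found no section that defines an all-treated set for that goal.

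**The concern.** A toxicity profile should describe what happened to the people who took the drug. Under 16.323 a dosed patient disappears from the rates once any single entry criterion proves to have been unmet, even though 13.5 has that patient's data in hand.

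The filter is not neutral with respect to toxicity. Section 3.16 sets laboratory and liver limits, including "Concomitant elevations in bilirubin and ALT above 1.0 x ULN (upper limit of normal) is not permitted". Section 3.25 excludes uncontrolled hypertension and cardiac illness, 3.29c excludes a long QTc, 3.29d excludes patients "Receiving any medications or substances with risk of torsades de pointes", and 3.39i excludes CYP3A4 inhibitors. A patient who fails one of these still has non-clear cell renal cancer and so belongs to the population in goal 2.23, but may carry a different toxicity risk. The direction of any bias is unknown.

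In a trial of about 39 patients, one exclusion can decide whether a rare event appears in the tables at all. Section 16.5 commits the secondary endpoints to public results reporting, so the omission would carry through to the published rates.

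**Working it through.** **Inputs**

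- Evaluable target: 35 (16.22 and 16.24).
- Extra patients, from 16.22: "We anticipate accruing an additional 4 patients to account for ineligibility, cancellation, major treatment violation, or other reasons". The total is 35 + 4 = 39, which agrees with the accrual table in 16.63.
- The plan states no size for the adverse-event set and no expected number of dosed but ineligible patients, so there is no figure of its own to reproduce on this point.
- Assumption: all N = 39 are dosed and k = 1, 2, 3 or 4 of them are later ruled ineligible. k = 0 is possible and gives no effect.
- Assumption: an ineligible patient's risk is RR times that of an eligible one, with RR = 0.5, 1 or 2.

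**Chance that a single event is lost.** Suppose exactly one of the N dosed patients has a given rare event. The probability that this is an excluded patient is

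P = RR·k / (N − k + RR·k).

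| k | RR = 0.5 | RR = 1 | RR = 2 |
|---|---|---|---|
| 1 | 0.5/38.5 = 1.3% | 1/39 = 2.6% | 2/40 = 5.0% |
| 2 | 1/38 = 2.6% | 2/39 = 5.1% | 4/41 = 9.8% |
| 3 | 1.5/37.5 = 4.0% | 3/39 = 7.7% | 6/42 = 14.3% |
| 4 | 2/37 = 5.4% | 4/39 = 10.3% | 8/43 = 18.6% |

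The 39 is a plan and not a cap, since 16.313 foresees over-accrual. With N = 42 and RR = 1 the range is 1/42 = 2.4% to 4/42 = 9.5%.

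**What the table would show for a rare event.** Take k = 2, with one of the two having the event.

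- Under 16.323: 0/37 = 0%. The exact (Clopper-Pearson) two-sided 95% upper limit is 1 − 0.025^(1/37) = 9.5%.
- With all dosed patients: 1/39 = 2.6%, upper limit 13.5%.

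**What it would show for a commoner event.** Take k = 4 and an assumed 7 events among the 35 eligible patients.

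- Under 16.323: 7/35 = 20.0%.
- With all dosed patients: from 7/39 = 17.9% if none of the four had the event to 11/39 = 28.2% if all four did.

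**Comparison with other parts of the plan.** The first limb of the stopping rule in 16.42 counts the first 15 treated patients, with no eligibility condition. Expedited reporting (10.4, 10.51) and data safety monitoring board review (16.41) have none either. Of these provisions, only the adverse-event rates in 16.323 apply the eligibility filter, so monitoring and final tables could rest on different patients.

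**The case against.** The best case for leaving the text alone has five parts.

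1. **The number may be zero.** Section 6.3 checks eligibility before registration is accepted, and the four spare patients also cover cancellations, who are never dosed, and major violations. This stands. k = 4 requires every spare patient to be both dosed and ineligible, and the relative risks of 0.5 and 2 have no source in the documents.

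2. **One route to late ineligibility fits the filter.** Section 18.1 allows 30 days after registration for pathology material used for central review and eligibility, while 6.5 requires treatment to begin within 14 days. Someone excluded on histology does not have non-clear cell disease and lies outside goal 2.23. This stands for that subgroup, although 17.0 lists no pathology considerations, so it is unclear whether the review operates. It does not cover patients who fail a laboratory, cardiac or concomitant-drug criterion.

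3. **Safety oversight is intact.** The stopping rule counts treated patients, and serious events are reported whatever the eligibility. This is correct, and it limits the point to the descriptive tables. It does not supply a population for those tables.

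4. **Events could still be listed or narrated.** Section 16.323 restricts rates and does not forbid a listing. But nothing in the plan calls for one, so it cannot be relied on.

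5. **The efficacy sections use the same eligible-and-treated set, and ineligible patients have shorter data.** Consistency with 16.311 and 16.321 suggests a convention, but one better suited to efficacy than to toxicity. Required data stop at confirmation of ineligibility, so adding these patients can lower crude rates slightly. That cost is real. A footnote discloses it without removing it.

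**Conclusion.** The concern holds, as a minor one. As written, 16.323 excludes toxicity data that 13.5 requires to be submitted, using a filter that is partly made of safety criteria. Confidence in this reading of the text is high.

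The consequence is probably small. The probabilities and rates above rest on an assumed 1 to 4 dosed but ineligible patients and on assumed relative risks, and they are conditional on the stated event pattern. No decision rule uses these rates, and the sample size of 35 and the primary endpoint do not depend on them. The direction of any bias cannot be determined from the documents.

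**What to change.** Replace the population sentence in 16.323 with: *All patients who receive at least one dose of pazopanib, regardless of eligibility, are included in adverse-event summaries.*

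Add a table footnote that marks events in ineligible patients, names the criterion not met (which separates a histology failure from a safety-criterion failure), and states that their data end when ineligibility was confirmed under 13.5. The eligible-and-treated set can stay as it is for the primary endpoint and response.

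The cost is one sentence and one footnote, with no extra patients, tests or data collection. The drawback is that a few patients in the tables may lie outside the target population or have shorter observation, and the footnote makes this visible.

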Grade 1	For hemoptysis, interrupt pazopanib and contact the Novartis Study Physician to discuss whether further treatment with pazopanib is appropriate. For other Grade I hemorrhage/bleeding events, continue pazopanib at the current dose; monitor as clinically indicated.
Grade 2	Step 1. If pulmonary or GI bleed (other than hemorrhoidal bleeding), discontinue pazopanib and continue follow-up per protocol. Otherwise, interrupt pazopanib until the AE resolved to \leq Grade 1. Step 2. Restart pazopanib ; consider reducing dose and monitor as clinically indicated.
Grade 3 or 4, or Recurrent \geq Grade 2 event after dose interruption/reduction.	Discontinue pazopanib and continue with follow-up per protocol.
Venous Thrombosis (DVT, PE)	
Grade 2	Continue pazopanib at the current dose; monitor as clinically indicated
Grade 3	Step 1. Interrupt pazopanib . Step 2. Initiate and monitor anticoagulation as clinically indicated. Step 3. Resume pazopanib at reduced dose only if all of the following criteria are met: 
 • The subject must have been treated with anticoagulant at the desired level of anticoagulation for at least one week. • No Grade 3 or 4 or clinically significant Grade 2, hemorrhagic events have occurred while on anticoagulation treatment. Subject should be monitored as clinically indicated during anticoagulation treatment and after resuming study treatment. When treating with warfarin, international normalized ratio (INR) should be monitored within three to five days after any change in pazopanib dosing (eg, re-initiating, escalating/de-escalating, or discontinuing pazopanib), and then at least weekly until the INR is stable. The dose of warfarin (or its derivatives) may need to be adjusted to maintain the desired level of anticoagulation
Grade 4 and/or PE	Discontinue pazopanib and continue follow-up per protocol.
Arterial Thrombosis/Ischemia	
Any Grade	Discontinue pazopanib and continue follow-up per protocol.
Thrombocytopenia: Investigate and document underlying cause	
Grade 1 or 2	Continue pazopanib with current dose; monitor as clinically indicated.
Grade 3 or 4	Step 1. Interrupt pazopanib until toxicity resolves to \leq Grade 2.

	Step 2. Restart pazopanib dose-reduced by 200 mg and monitor as clinically indicated. If no recovery to \leq Grade 2 or recurrent Grade 3 or 4 thrombocytopenia, discontinue IP and follow-up per protocol.

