SAEs brought to the attention of the investigator at any time after cessation of pazopanib and considered by the investigator to be related or possibly related to pazopanib must be reported to Novartis if and when they occur. Additionally, in order to fulfill international reporting obligations, SAEs that are related to study participation (e.g., procedures, invasive tests, change from existing therapy) or are related to a concurrent medication will be collected and recorded from the time the subject consents to participate in the study until he/she is discharged.

- 10.6 Adverse events to be graded at each evaluation and pretreatment symptoms/conditions to be evaluated at baseline per the CTCAE v4.0 grading unless otherwise stated in the table below:

System Organ Class (SOC)	Adverse event/Symptoms	Baseline	Each evaluation
Gastrointestinal Disorders	Baseline number of stools per day	X	
	Diarrhea		X
Vascular Disorders	Hypertension	X	X
General disorders and administration site conditions	Fatigue	X	X
Investigations	Alanine aminotransferase increased	X	X
	Aspartate aminotransferase increased	X	X
	Blood bilirubin increased	X	X
	Lymphocytes decreased	X	X
Metabolism and Nutrition Disorders	Hypophosphatemia	X	X
	Hyponatremia	X	X
	Hypomagnesemia	X	X

10.61 Submit via appropriate MCCC Case Report Forms (i.e., paper or electronic, as applicable) the following AEs experienced by a patient and not specified in Section 10.6.

10.611 Grade 2 AEs deemed *possibly, probably, or definitely* related to the study treatment or procedure.

10.612 Grade 3 and 4 AEs regardless of attribution to the study treatment or procedure.

10.613 Grade 5 AEs (Deaths)

10.6131 Any death within 30 days of the patient's last study treatment or procedure regardless of attribution to the study treatment or procedure.

10.6132 Any death more than 30 days after the patient's last study treatment or procedure that is felt to be at least possibly treatment related must also be submitted as a Grade 5 AE, with a CTCAE type and attribution assigned.

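### The adverse event table in 16.323 has no grade limit, but outside the ten terms in 10.6 low-grade events are only partly collected, so their any-grade rates will be understated

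*Combined protocol and SAP*

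**What the plan says.** Secondary goal 2.23 is "To describe toxicity profile of pazopanib in non clear cell metastatic renal cell cancer patients". The analysis serving it is in 16.323: "The maximum grade for each type of adverse event will be recorded for each patient". Frequency tables are then reviewed for patterns, with relationship to treatment taken into account. No grade threshold or attribution filter is stated, and no term is treated differently from another.

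Collection is set elsewhere. The 10.6 table is introduced as "Adverse events to be graded at each evaluation and pretreatment symptoms/conditions to be evaluated at baseline per the CTCAE v4.0 grading". It lists ten graded terms for each evaluation: diarrhea, hypertension, fatigue, ALT, AST, bilirubin, lymphocytes, and low phosphate, sodium and magnesium. Section 10.61 then covers "the following AEs experienced by a patient and not specified in Section 10.6" and asks for three groups:

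- Grade 2 at least possibly "related to the study treatment or procedure" (10.611);
- "Grade 3 and 4 AEs regardless of attribution to the study treatment or procedure" (10.612);
- Grade 5, meaning deaths within 30 days of last treatment, or later if at least possibly related (10.613).

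The routine form during treatment in 18.1 is the solicited adverse event form. Section 10.11 adds that anything reported by the expedited route must also go through routine reporting.

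**The concern.** For a term outside 10.6, a Grade 1 event, or a Grade 2 event judged unlikely or unrelated, normally has no line in the database. In a maximum-grade table that patient cannot be told apart from one who had no event. The same table would show diarrhea and hypertension at every grade beside nausea and vomiting cut off by grade and attribution, with nothing to mark the difference.

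The omitted terms are ones the protocol expects. Section 10.31 names nine expected events, and six are absent from 10.6: abdominal pain, nausea, vomiting, anorexia, headache and hair color changes. Section 15.17 lists all six (hair color as depigmentation), and asthenia, as very common in renal cell carcinoma.

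For unlisted Grade 2 events the attribution filter acts at collection, so the analysis cannot revisit it. The attribution check in 16.42 covers only Grade 4 and 5. Section 16.5 commits secondary endpoints to public results reporting, where a reader would take the any-grade columns at face value.

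**Working it through.** **Inputs.** Counts are from Appendix VII Table 14 (VEG105192, pazopanib arm, n = 290). List membership is from 10.6. The planned number of evaluable patients is 35 (16.22).

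**Formulas.** Any-grade rate = count / 290. Grade 1-2 = any grade − Grade 3 − Grade 4. Expected number in this trial = 35 × count / 290. The subtraction assumes no Grade 5 among these terms in the pazopanib arm; the only term-level Grade 5 that the footnotes mention is asthenia on placebo.

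**Plan's own figures first.** All twelve any-grade percentages in Table 14 reproduce after rounding, for example 150/290 = 51.7% (printed 52) and 109/290 = 37.6% (printed 38).

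| Term | In 10.6? | Any grade | Grade 3-4 | Grade 1-2 (share) | Expected in 35, any grade | Expected in 35, Grade 3-4 |
|---|---|---|---|---|---|---|
| Diarrhea | yes | 150 (51.7%) | 11 | 139 (93%) | 18.1 | 1.3 |
| Hypertension | yes | 115 (39.7%) | 13 | 102 (89%) | 13.9 | 1.6 |
| Hair color changes | no | 109 (37.6%) | 1 | 108 (99%) | 13.2 | 0.1 |
| Nausea | no | 74 (25.5%) | 2 | 72 (97%) | 8.9 | 0.2 |
| Anorexia | no | 65 (22.4%) | 6 | 59 (91%) | 7.8 | 0.7 |
| Vomiting | no | 61 (21.0%) | 7 | 54 (89%) | 7.4 | 0.8 |
| Fatigue | yes | 55 (19.0%) | 7 | 48 (87%) | 6.6 | 0.8 |
| ALT increased | yes | 53 (18.3%) | 21 | 32 (60%) | 6.4 | 2.5 |
| AST increased | yes | 43 (14.8%) | 14 | 29 (67%) | 5.2 | 1.7 |
| Asthenia | no | 41 (14.1%) | 8 | 33 (80%) | 4.9 | 1.0 |
| Abdominal pain | no | 32 (11.0%) | 6 | 26 (81%) | 3.9 | 0.7 |
| Headache | no | 30 (10.3%) | 0 | 30 (100%) | 3.6 | 0.0 |

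**Totals for the seven unlisted terms.** Any grade: 109 + 74 + 65 + 61 + 41 + 32 + 30 = 412. Grade 3-4: 1 + 2 + 6 + 7 + 8 + 6 + 0 = 30. Grade 1-2: 412 − 30 = 382, and 382/412 = 93%. The five listed terms sum to 416, so the unlisted terms are 412/828 = 50% of all counts in the table.

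**Range of the observed any-grade rate.** The lower end keeps Grade 3-4 only; the upper end keeps everything. Hair color runs from 0.3% to 37.6%, nausea 0.7% to 25.5%, anorexia 2.1% to 22.4%, vomiting 2.4% to 21.0%. The position inside each range depends on how many Grade 1-2 events are related Grade 2, which the documents do not give. As an illustration only, losing half of Grade 1-2 gives (109 − 54)/290 = 19.0%, (74 − 36)/290 = 13.1%, (65 − 29.5)/290 = 12.2% and (61 − 27)/290 = 11.7%.

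**Side by side.** Hypertension and hair color change had similar any-grade rates (39.7% and 37.6%). In 35 patients about 13.9 and 13.2 would be expected. The plan captures the first in full; for the second, the number guaranteed regardless of attribution is 0.1.

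**The case against.** The best defense is that full collection for a short list, with thresholds elsewhere, is a stated and deliberate rule for a drug already approved in this disease. On that view 16.323 simply tabulates what is collected. The analysis is descriptive, and no comparison with Appendix VII is planned. This stands as a defense of the collection rule. It does not defend a table that gives no sign of the rule.

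Four stronger readings are tempting, and the documents do not support them.

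- *The commonest effects as a group are understated.* They are not. Diarrhea and hypertension, the two commonest in Table 14, and fatigue, ALT and AST are graded at every evaluation and lose nothing.
- *Unlisted low-grade events are never recorded.* This is too absolute. Expedited events, including Grade 1-2 with hospitalization of at least 24 hours (10.4), also enter routine reporting, and laboratory and treatment data have their own forms. Grade 1 hemoptysis is not in 10.6 although 8.3 says "For hemoptysis, interrupt pazopanib and contact the Novartis Study Physician"; it may lack an adverse event line, but the interruption should show on the treatment form.
- *The 93% is the size of the loss.* It is only the ceiling. Investigators have grounds in 15.17 to call these events related, and related Grade 2 is kept, so for true drug effects the loss is mainly Grade 1.
- *The schedule leaves a data gap at end of treatment.* The row "Adverse event assessment" in 4.0, as far as its columns can be read, is marked on Day 1 of each cycle and not at end of treatment. Section 18.1 already requires the form then, so this is a schedule inconsistency and no more.

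**Conclusion.** The mismatch holds. Followed as written, 16.323 yields any-grade rates that are too low for terms outside 10.6. Those terms include the third to sixth commonest in Table 14 (hair color change, nausea, anorexia, vomiting), and asthenia, abdominal pain and headache.

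If Table 14 rates carried over to this population, 35 evaluable patients would include about 13 with hair color change, 9 with nausea, 8 with anorexia and 7 with vomiting. Capture regardless of attribution is below one patient for each. The number actually tabulated will lie between these limits and cannot be fixed more closely from the documents.

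Grade 3-4 rates are not affected. The stopping rule in 16.42 is not affected either, since it counts related events of Grade 4 or higher. The consequence is confined to a descriptive secondary objective, but the reported rates would mislead, and correcting this costs little.

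**What to change.** 1. **In 16.323:** tabulate all grades only for the ten 10.6 terms. For every other term, report Grade 3 and above (Grade 5 as 10.613 defines it), with related Grade 2 in a separate column and no any-grade total. State the collection rule in the table title or footnote. This costs wording only and works for data already collected.
2. **In 10.6, for patients still to be treated:** add nausea, vomiting, anorexia, hair color change, asthenia, abdominal pain and headache, at baseline and at each evaluation. Adding only some of the seven would leave the mixed table in place. The cost is a few more form lines per visit. The note in 14.0 shows that specimens were collected before addendum 7, so some patients may already have been followed under the present rule; they must be reported separately under it.
3. **In 4.0:** mark adverse event assessment in the end-of-treatment column so that it agrees with 18.1. This adds no data collection.
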